11.1 Missing Efficacy Data

Missing Week 24 values of sPCR will be imputed using a multiple imputation (MI) procedure for the primary analysis of primary efficacy endpoint and using a last observation carried forward (LOCF) as sensitivity analysis. The details of imputation methods are described in the analysis of efficacy section.

Missing data for the secondary endpoints will not be imputed.

11.2 Adverse Events Missing Data

Treatment-emergent adverse events (TEAEs) with missing severity will be considered severe and TEAEs with missing relationship will be counted as related.

In cases where the start date is not complete, the assumption will be made that the adverse event is a treatment-emergent event unless there is evidence to the contrary. The first treatment start date will be used as the AE start date if the start date is missing. Missing AE end date will not be imputed. The AE will be assumed as ongoing if end date is missing.

11.3 Concomitant Medications Missing Dates

In cases where the start or stop dates are not complete, the assumption will be made that the medication is a concomitant medication unless there is evidence to the contrary.

If year and month of the dates are available (and only day is missing) the first day of the month will be used to impute start date, and the last day of the month will be used to impute stop date.

If only the year is available and it is before the year of first study treatment date, January will be used to impute the start date and December will be used to impute the stop date. If the year is equal to the year of the first study treatment date, month and day of the first study treatment date

will be used to impute the start date, and month of the last study treatment date will be used to impute the stop date.

If the start or stop date is completely missing, use the first study treatment date to impute the start date, and the last study treatment date to impute the stop date.

Imputed dates will be used for categorization of medications to concomitant or prior, but data listings will present the date as recorded on the CRF.

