17. Have a condition or be in a situation that the Investigator feels may put the subject at significant risk, may confound the study results, or may interfere significantly with the subject's participation in the study.
18. Have a known allergy and/or sensitivity to the study drug or its excipients.

Investigational Product: Fostamatinib (100 mg and 150 mg tablets) and matching placebo

Route of Administration: Oral

Dose: 1 tablet PO or matching placebo

Frequency of Dosing: *bid*

Duration of Treatment: 24 weeks (extended treatment available to eligible subjects)

Statistical Methods:

Analysis Populations:

- Intent-to-Treat Population

The Intent-to-treat (ITT) population will include all randomised subjects. All efficacy endpoints will be analyzed based on the ITT population, and subjects will be analyzed according to their randomised treatment assignment. The efficacy analyses based on the ITT population will be considered the primary efficacy analyses.

- Per-Protocol Population

The Per-Protocol (PP) population will include all subjects in the ITT population who had no major protocol violations. Major protocol violations will include:

- Not receiving any study treatment
- Not receiving the correct study treatment
- Not receiving sufficient treatment
- Failing to meet eligibility criteria
- Other major protocol violations, as determined by a blinded review of the data prior to database lock

Baseline measurements will be the last measurement for the corresponding variable prior to the first randomised dose at Visit 2. For analysis of the primary efficacy endpoint, the main analysis will be performed with baseline defined as the average between Visit 2 and the most recent screening value prior to Visit 2 (a secondary analysis, with the Visit 2 value alone as baseline, will be performed).

- Safety Population

The safety population will include all randomised subjects who received at least 1 dose of the allocated study drug. The safety population will be used for analysis of all safety assessments. The subjects will be analyzed as treated.

Primary Efficacy Endpoint:

- Mean change from Baseline of proteinuria as measured by sPCR at 24 weeks (Visit 9)

Secondary Efficacy Endpoints:

- Mean change from pre-treatment to post-treatment in mesangial hypercellularity on renal biopsies.
- Percentage of subjects with $\geq 50\%$ reduction in sPCR from Baseline (Visit 2) at Week 24 (Visit 9).

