R_i = total number of tablets returned for visit interval i

$T_i = 2$ for bid dosing and $=1$ for qd dosing, for visit interval i

P_i = total number of days in visit interval i .

The total number of tablets that were supposed to be taken during the double-blind treatment period excludes the number of tablets not taken due to a dose interruption. If a patient fails to return a study drug kit dispensed during the double-blind treatment period, then study drug compliance is considered to be missing.

Baseline sPCR: Two baseline sPCR value will be used in the analysis. In primary efficacy analysis, the baseline sPCR is defined as the average of non-missing value between Visit 2 and the most recent screening value prior to Visit 2. If only one non-missing sPCR is available, this value will be used as baseline.

A **Treatment-Emergent Adverse Event (TEAE)** is any adverse event that emerges on or after first dosing and prior to the end of follow-up (having been absent prior to treatment) or worsens relative to the pre-treatment state.

Hy's Law criteria are: concurrent aspartate aminotransferase (AST) or alanine aminotransferase (ALT) $\geq 3x$ upper limit of normal (ULN) with total (and/or direct/conjugated) bilirubin (TBL) $> 2x$ ULN and alkaline phosphatase (ALP) $< 2x$ ULN, and no other reason can be found to explain the combination of increased aminotransferase and serum total bilirubin, such as viral hepatitis, alcohol abuse, ischemia, preexisting liver disease, or another drug capable of causing the observed injury.

Prior Medications will be defined as the medications used prior to the first dose of study drug. If the medication is used both prior to and on/after the first dose of study drug, the medication is both prior medication and concomitant medication.

Concomitant Medication will be defined as the medications used on/after the first dose of study drug.

7. Statistical Methods

The statistical analysis of the data obtained from this study will be performed using SAS® version 9.4 or higher. All inferential tests will be 2-sided and will be performed using a type I error rate of 5%, unless otherwise indicated.

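### For treatment courses that cross New Year, the year-only stop-date rule in SAP 11.3 imputes a stop date before first dose, which can class a drug used on study as prior only

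*SAP*

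**What the plan says.** SAP 11.3 opens with a default for incomplete dates: "the assumption will be made that the medication is a concomitant medication unless there is evidence to the contrary". It then gives branches by how much of the date is known.

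- **Day missing:** first of the month for a start, last of the month for a stop.
- **Only the year known, before the first-dose year:** January for a start, December for a stop.
- **Only the year known, equal to the first-dose year:** the start clause reads "If the year is equal to the year of the first study treatment date, month and day of the first study treatment date", and the stop clause reads "month of the last study treatment date will be used to impute the stop date".
- **Date completely missing:** the first treatment date for a start, and for a stop "the last study treatment date to impute the stop date".

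The section closes by giving the imputed values a purpose: "Imputed dates will be used for categorization of medications to concomitant or prior". Listings keep the date as recorded.

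SAP section 6 (Analytic Definitions) says that a concomitant medication "will be defined as the medications used on/after the first dose of study drug". It adds: "If the medication is used both prior to and on/after the first dose of study drug, the medication is both prior medication and concomitant medication". SAP 7.2 summarises prior and concomitant medications by treatment in the ITT population.

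**The concern.** In the third branch the stop date combines two sources: the year comes from the record and the month from the last dose. These agree only if first and last dose fall in the same calendar year. Treatment lasts 24 weeks, so many courses will not meet that condition, and the clause makes no allowance for it.

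An imputed stop before first dose matters because imputed dates are used for categorisation. Take a drug that was started before the study and stopped some weeks into treatment. Under SAP section 6 it is both prior and concomitant. With its stop date moved to before first dose, it would drop out of the concomitant summary. The SAP 7.2 count of subjects who changed their antihypertensive regimen during treatment could also be affected, if imputed dates are used there; the SAP does not say whether they are.

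**Working it through.** The documents give no figure on this point, so the check applies the written rule to dates.

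**Inputs**
- Course length L = 24 weeks = 168 days (Protocol synopsis). The Week 24 visit window of ±7 days gives 161 to 175 days.
- Last dose = first dose + (L − 1) days.
- Imputed stop = year of first dose, month of last dose. The clause gives no day, so the first of the month, the last of the month and the day of last dose were all tried.
- Assumption: first doses spread evenly over the year. For the enumeration, every day of 2014 to 2017 was used (1,461 days).

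**1. How often a course crosses New Year.** At 168 days, in a non-leap year, this happens for first doses from 18 July to 31 December: 14 + 31 + 30 + 31 + 30 + 31 = 167 days, and 167/365 = 45.8%. Enumeration over the four years gives 668/1,461 = 45.7%. At 161 days it is 640/1,461 = 43.8%, and at 175 days 696/1,461 = 47.6%.

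**2. What the rule gives for those courses.** Last dose falls 167 days after first dose. The same calendar day in the first-dose year is therefore 365 − 167 = 198 days before first dose (199 where a leap day intervenes). Moving to the end of that month gains at most 30 days: 198 − 30 = 168. So the imputed stop is always at least 168 days before first dose. Enumeration agrees:

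| Day used for the stop | Days before first dose (L = 168) | Share of crossing courses with stop before first dose |
|---|---|---|
| Last of month | 168 to 199 | 100% |
| Day of last dose | 198 to 199 | 100% |
| First of month | 198 to 229 | 100% |

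The 100% held at every course length tried from 28 to 182 days. Among the lengths tried from 84 to 182 days, courses that stay within one calendar year never gave a stop before first dose.

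**3. Example.** First dose 10 Oct 2016; adding 167 days gives last dose 26 Mar 2017. A recorded stop of 2016 becomes March 2016. Counted from 31 March that is 193 days before first dose; from 1 March it is 223.

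**4. Classification, by what is known of the start date**
- *Start known to be before first dose, true stop during treatment (say December 2016):* the imputed dates leave no use on or after first dose, so the drug is prior only. Its true class is both.
- *Start also year-only, 2016:* the start is imputed as 10 Oct 2016, and the stop precedes it. The dates contradict each other and the class is undefined.
- *True stop in 2016 before first dose:* prior only is correct.

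**5. Exposure.** The share of records with a year-only stop date in the first-dose year is not given. At an assumed 1%, 0.01 × 45.7% = 0.46% of records; at 5%, 0.05 × 45.7% = 2.3%. These records meet the rule; only some of them would be misclassified.

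**The case against.** The best defence is the opening default. Incomplete dates mean concomitant unless there is evidence otherwise, and a date produced by imputation is not evidence. If the default governs, no drug is misclassified. That stands as far as it goes, so a reader should not infer that the plan certainly classes on-study drugs as prior. But the closing sentence gives the sorting to the imputed dates, and nothing says which sentence prevails. The impossible date remains either way.

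A programmer might also take both year and month from the last dose. The text does not say that: the branch for a wholly missing stop uses the full last-dose date, whereas this one borrows only the month. Borrowing the year too would overwrite a recorded 2016 with 2017.

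Three stronger readings are tempting, and the documents do not support them:

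- *The error always removes drugs that belong on the concomitant list.* A drug that truly stopped that year before first dose is correctly prior. Protocol 7.6 has concomitant therapies recorded at Visits 1b through 10, so year-only stops may mostly concern pre-study drugs.
- *It undermines the review of restricted medications or the reading of the sPCR result.* The SAP describes no restricted-medication review based on imputed dates; SAP 7.1 tabulates the major deviations recorded on the case report forms. SAP 7.2 does not tie the antihypertensive count to sPCR.
- *Year-only dates in the second treatment year are a further source of error.* No branch covers them, but any such date is after first dose, so the drug is concomitant without imputation.

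If the last treatment date were read to include extended treatment, the failure would be less regular: 9% of courses at 400 days and 37% at 500 days. SAP section 1 limits the plan to the main study.

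**Conclusion.** The stop-date clause is wrong as written. For every 24-week course that crosses New Year it yields a stop 168 to 229 days before first dose, depending on first-dose date and the unstated day of the month. Such courses make up about 46% of first-dose dates (44-48% across the visit window), assuming even enrolment. Prior-only misclassification follows when the start is before first dose, the drug was in fact used on study, and the imputed date is allowed to override the default.

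The consequence is minor. It reaches the descriptive prior and concomitant medication tables, and the antihypertensive-change count if that uses imputed dates. No primary or secondary efficacy analysis uses a stop date, and the RAS-blockade subgroup in SAP 7.4.3 uses start dates. The exposure of about 0.5-2.3% of records rests on the assumed 1-5%.

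**What to change.** In SAP 11.3:

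1. Leave the year-only start-date clause as it is. The RAS-blockade subgroup in SAP 7.4.3 relies on imputed start dates, so that clause must not be lost in the edit.
2. Replace only the stop-date clause with: *the earlier of 31 December of that year and the last study treatment date will be used to impute the stop date.* For a course that crosses New Year this gives 31 December of the first-dose year, which is never before first dose. In the example the stop becomes 31 Dec 2016 and the drug is concomitant.
3. Add that an imputed stop date may not precede the start date. This also covers a drug started after the last dose but in the same year.
4. State that the default to concomitant prevails unless recorded, not imputed, information shows that the drug stopped before first dose.

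The cost is a few lines of SAP text and a small programming change, with no effect on the efficacy analyses. Some drugs that truly stopped before first dose will be counted as concomitant; the section's default already accepts that.

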12. REFERENCE

1. Little, R.J.A. and Rubin, D.B. (1987), *Statistical Analysis with Missing Data*, New York: John Wiley & Sons, Inc
2. Yang C. Yuan, *Multiple Imputation for Missing Data: Concepts and New Development*, P267-25, SAS Institute Inc., Rockville, MD

13. Appendices

A. Error! Reference source not found. **Timeline**

Main Study (Visit 1 through 10)

Study Procedure	Screening		Double-Blinded Treatment Period							Follow-Up		
	Visit 1a	Visit 1b	Visit 2	Visit 3	Visit 4	Visit 5	Visit 6	Visit 7	Visit 8	Visit 9/ Withdraw	Visit 10	
	Up to 120 days prior to Baseline	Up to 30 days prior to Baseline	Day 1 (Baseline)	Week 1 (±3 days)	Week 2 (±3 days)	Week 4 (±3 days)	Week 8 (±4 days)	Week 12 (±4 days)	Week 18 (±7 days)	Week 24 (±7 days)	Week 26 (±3 days)	
Informed Consent	X											
Demographic Information		X										
Medical History ¹		X	X									
Submit pre-study renal biopsy to central path for assessment ²	X											
Physical Exam ³		X	X	X	X	X	X	X	X	X	X	X
Inclusion/Exclusion		X	X									
Vital Signs ⁴		X	X	X	X	X	X	X	X	X	X	X ¹⁰
Haematology ⁵		X	X	X	X	X	X	X	X	X	X	X ¹⁰
Serum Chemistry ⁶		X	X	X	X	X	X	X	X	X	X	X ¹⁰
Plasma Pharmacokinetics												
Serum Pregnancy ⁷		X	X									
Urine for Pregnancy ⁷			X									
Urinalysis ⁸		X	X	X	X	X	X	X	X	X	X	X ¹⁰
Urine for sPCR		X	X	X	X	X	X	X	X	X	X	
Serum IgA			X									
Renal biopsy												
Concomitant Medications		X	X	X	X	X	X	X	X	X	X	X
Adverse Event Evaluation ⁹			X	X	X	X	X	X	X	X	X	X
Study Drug Accountability			X	X	X	X	X	X	X	X	X	X
Dispense Study Drug			X	X	X	X	X	X	X	X	X	X

Medical History at Screening (Visit 1b) includes documentation of date of initial IgAN diagnosis, documentation of most recent renal biopsy, concomitant medications, documentation of angiotensin blockade treatment, prior medications for treatment of IgAN, and any other relevant medical condition.

² Histologic eligibility must be confirmed using the most recent biopsy obtained within 180 days prior to the initial study visit (Visit 1a) before performing any additional study specific screening procedures.

³ Physical Examination includes HEENT, cardiovascular, dermatological, musculoskeletal, respiratory, gastrointestinal and neurological systems. Baseline (Visit 2) will also include a measurement of height and weight.

⁴ Vital Signs include blood pressure and heart rate measured as noted in Section **Error! Reference source not found.**

- ⁵ Haematology includes red blood cell count (RBC), white blood cell count (WBC), hemoglobin, hematocrit, WBC differential count (neutrophils, lymphocytes, eosinophils and basophils), MCHC, MCH, MCV, MPV, RDW, and platelet count.
- ⁶ Serum Chemistry includes Na, K, Cl, CO₂, Ca, P, BUN, creatinine, globulin, glucose, ALT, AST, LDH, alkaline phosphatase, total bilirubin, direct bilirubin, indirect bilirubin, total protein and albumin.
- ⁷ Females of childbearing potential only. Females who are either post-menopausal for at least 1 year or surgically sterile (documented by medical record) do not need to take pregnancy tests. In Austria only, at-home urine pregnancy testing will be completed at Week 15 and Week 21, as described in Section Error! Reference source not found.
- ⁸ Urinalysis includes appearance, glucose, ketones, blood, protein, nitrite, bilirubin, specific gravity, pH, urobilinogen, and leucocyte esterase. If positive for blood or protein trace, microscopy will be included.
- ⁹ SAEs will be followed to resolution or stabilization unless the subject is lost to follow-up.
- ¹⁰ Haematology, serum chemistry and urinalysis only performed at Week 26 (Visit 10) if there are clinically significant abnormalities identified at Week 24 (Visit 9).
- ¹¹ Visit 9 renal biopsy should be collected within 14 days of Visit 9, and is not required to be collected during this visit itself; Visit 9 biopsy will not be required for subjects that withdraw early.

B. Laboratory Test

Normal ranges for each parameter in hematology and serum chemistry will be used to categorize the test results as low (value lower than the lower limit of normal [LLN]), normal (value within the normal range), or high (value higher than the upper limit of normal [ULN]).

The table below provides the normal values for urinalysis tests. Any values other those listed will be considered “abnormal” for the purpose of shift tables presentation.

Urine Dipstick Test Name	Normal Reference Range	
	Low	High
Appearance	Clear	Clear
bilirubin	Negative	Negative
Blood	Negative	Negative
Glucose	Negative	Negative
Ketones	Negative	Negative
Leukocyte Esterase	Negative	Negative
Nitrite	Negative	Negative
pH	5	8
Protein	Negative	Negative
Specific Gravity	1.001	1.035
Urobilinogen	Normal	Normal
Urine Microscopy	Normal	Normal

C. Error! Reference source not found. Pressure

The 2017 ACC/AHA guidelines will be followed for the analysis of blood pressure data. The following classification will be followed:

Systolic and Diastolic Blood Pressure Abnormalities

Classification	Upper Limit of Blood Pressure (mm Hg)	
	Systolic	Diastolic
Normal	less than 120	and Less than 80
Elevated	120 – 129	and Less than 80
Stage 1	130 – 139	or 80 – 89
Stage 2	140 or Higher	or 90 or Higher
Hypertensive Crisis	Higher than 180	or Higher than 120

If a subject’s blood pressure satisfies more than one classification, the more severe classification will be assigned. Classifications above are ordered in from less severe to most severe.

For the purpose of analysis of shift in vital signs will be considered normal according to the following cut offs:

Vital Sign Normal Ranges

Vital Sign	Normal Range
Systolic/Diastolic blood pressure	Less than 120/80 mm Hg
Heart rate	50 – 100 beats/min

D. Assessment of Renal Biopsies

The following data will be obtained for each biopsy:

- Total number of glomeruli (a minimum of 8)
- Number of glomeruli with global sclerosis
- Number of glomeruli with segmental sclerosis

For each glomerulus in the biopsy the following will be assessed (see Table 6):

- Mesangial hypercellularity
- Endocapillary hypercellularity (absent, segmental or global)
- Presence of crescents (cellular/fibrocellular or fibrous)

From the above assessments a MEST score will be calculated.

Table 6: Oxford Classification of Renal Biopsy Scoring

Variable	Definition	Score
Mesangial hypercellularity	<4 Mesangial cells/mesangial area=0	M0
	4–5 Mesangial cells/mesangial area=1	M1
	6–7 Mesangial cells/mesangial area=2	
	≥ 8 Mesangial cells/mesangial area=3	
	The mesangial hypercellularity score is the mean score for all glomeruli	
Segmental glomerulosclerosis	Any amount of the tuft involved in sclerosis, but not involving the whole tuft or the presence of an adhesion	S0-absent S1-present
Endocapillary hypercellularity	Hypercellularity due to increased number of cells within glomerular capillary lumina causing narrowing of the lumina	E0-absent E1-present
Tubular atrophy/interstitial fibrosis	Percentage of cortical area involved by the tubular atrophy or interstitial fibrosis, whichever is greater	T0-0-25% T1-26-50% T2->50%

E. Example SAS Code of Multiple Imputation

Step 1: Impute non-monotone missing visits using MCMC

```
proc mi data=TEMP seed=007 nimpute=10 out=OUTMI_1;
  mcmc impute=monotone chain=multiple;
  var trt1 trt2 endohbl base visit3--visit9;
run;
```

Step 2a: Impute monotone missing visit using a monotone regression model for non-placebo subjects who discontinued for reasons other than AE

```
proc mi data=OUTMI_1 seed=007 nimpute=1 out=OUTMI_2A;
  where trt01pn>1 & comp24wk^='ADVERSE EVENT';
  class trt01pn endohbl;
  monotone reg(visit9);
  var trt01pn endohbl base visit3--visit9;
run;
```

Step 2b: Impute monotone missing visit using a monotone regression model for placebo subjects or non-placebo subjects who discontinued due AE

```
proc mi data=OUTMI_1 seed=007 nimpute=1 out=OUTMI_2B;
  where trt01pn=1 or (trt01pn>1 & comp24wk='ADVERSE EVENT');
  class endohbl;
  monotone reg(visit9);
  var endohbl base visit3--visit9;
run;
```

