3.2 Determination of Sample Size

A sample size of 25 evaluable subjects in each of the 3 treatment groups will have an 80% power to detect a 43% reduction in sPCR from Baseline to Week 24 between the pooled fostamatinib and placebo groups, using a 2-sided t-test with $\alpha = 0.05$ and log-transformed data. This calculation assumes that the 3 treatment groups have the same mean and standard deviations of urinary protein/creatinine ratio and coefficient of variation of 0.923 at Baseline and that the values for the placebo group remain constant over 24 weeks. Treatment allocation ratio will be 1:2 for the placebo: combined fostamatinib groups

Table 1 Study Treatment

Treatment Group	Number of Subjects	Dose
C	25	Placebo bid
A	25	Fostamatinib 100 mg bid
B	25	Fostamatinib 150 mg bid

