7.4.1 Main Analysis

The primary efficacy endpoint will be analyzed using an analysis of covariance (ANCOVA) model based on the ITT population. The ANCOVA model will include both the treatment groups and the presence/absence of endothelial hypercellularity at baseline as factors and adjust for the sPCR at baseline (as a covariate). If required and when possible, missing Week 24 data will be imputed using an appropriate Multiple Imputation (MI) procedure. Should Multiple Imputation procedures fail, last observation carried forward (LOCF) will be used as an alternative imputation algorithm.

The regression method for monotone missing data (SAS PROC MI) will be used for multiple imputation. For patients who discontinued the study due to adverse events, consider the missing data mechanism for the missing change from baseline values to be missing not at random (MNAR). For patients who discontinued the study due to reasons other than adverse events or patients who completed the study but have missing data at a visit, consider the missing data mechanism for the missing change from baseline values to be missing at random (MAR).

Missing data will be imputed in two separate subgroups. The first subgroup will contain all patients randomized to a Fostamatinib group that have data available at the visit or have a MAR missing data mechanism. The second subgroup will contain all patients randomized to placebo as well as fostamatinib patients missing data at the visit with an MNAR missing data mechanism.

Multiple imputation will then be performed within each subgroup, resulting in missing data for Fostamatinib patients under an MAR missing data mechanism imputed from a model obtained only from Fostamatinib treated patients, and missing data from all placebo patients as well as Fostamatinib treated patients with an MNAR missing data mechanism imputed from a model obtained only from placebo treated patients. After obtaining complete data sets for both subgroups, the complete data sets after combining subgroups will be used in the analysis, and inferences from each complete dataset will be combined to obtain an overall test statistic.

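### The only number of imputations given for the primary analysis is 10, in example code, which leaves a primary p-value near 0.05 partly dependent on the random seed

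*SAP*

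**What the plan says.** SAP 7.4.1 makes multiple imputation part of the main analysis of the primary endpoint: "If required and when possible, missing Week 24 data will be imputed using an appropriate Multiple Imputation (MI) procedure". Imputation is done in two subgroups. One is fostamatinib subjects with Week 24 data or treated as missing at random. The other is placebo subjects plus fostamatinib subjects who stopped for adverse events. An ANCOVA is run on each completed dataset, and "inferences from each complete dataset will be combined to obtain an overall test statistic". SAP section 7 sets the test at two-sided 5%.

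Neither SAP 7.4.1 nor SAP 11.1 gives a number of imputations, a seed or a limit on Monte Carlo error. Protocol 10.3.1 and 10.8 defer the method to the SAP. The only figures are in SAP Appendix E, headed "Example SAS Code of Multiple Imputation". Step 1 reads "proc mi data=TEMP seed=007 nimpute=10 out=OUTMI_1". Step 2a reads "proc mi data=OUTMI_1 seed=007 nimpute=1 out=OUTMI_2A", and Step 2b has the same seed and also one draw. Each Step 1 dataset is thus completed once, so the intended total is m = 10. Neither Step 2a nor Step 2b shows a BY statement.

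LOCF is the fallback if imputation fails, and SAP 7.4.2 makes it the only imputation sensitivity analysis.

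**The concern.** A pooled multiple-imputation result carries random error from using a finite number of imputations. With m = 10 that error can be large enough to move a p-value across 0.05 when the answer that would be reached with very many imputations (the stable p) lies close to that line. Which side it falls on then depends partly on the seed.

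Small subgroups make this worse. In Step 2b the Week 24 value is regressed on the endocapillary factor, baseline and visits 3 to 8. That is 8 predictors, fitted on the observed Week 24 values of at most about 25 placebo subjects. The imputations are noisy and the fraction of missing information rises. What is at stake is how the primary result is read if it comes out borderline. The planned LOCF analysis would not show the seed dependence.

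**Working it through.** **Inputs from the documents.** m = 10 and seed 007 (SAP Appendix E); two-sided 5% (SAP section 7); 25 subjects per group, 1:2 placebo to pooled fostamatinib, CV 0.923, 43% reduction (SAP 3.2).

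**Assumed, because neither document gives it.** The share of Week 24 values missing, taken as 5% to 30%. Also assumed: correlations of 0.5 and 0.7 between visits, 40% of dropouts due to adverse events, and random dropout times.

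**The plan's own figure first.** SAP 3.2 states: "A sample size of 25 evaluable subjects in each of the 3 treatment groups will have an 80% power".
- SD of ln(sPCR) = sqrt(ln(1 + 0.923²)) = 0.785.
- Log difference = −ln(0.57) = 0.562.
- SE = 0.785 × sqrt(1/25 + 1/50) = 0.192, so the expected t is 0.562 / 0.192 = 2.92.
- Power is 83.2% (normal) or 82.2% (t, 73 df). The stated 80% is reproduced, slightly on the safe side.

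**Seed-to-seed spread, by formula.** The SD of the pooled t over seeds is about sqrt(FMI / m), where FMI is the fraction of missing information. For a stable p of 0.05, the 95% range over seeds runs over t = 1.96 ± 1.96 × SD:

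| FMI | SD at m = 10 | p range, m = 10 | SD at m = 100 | p range, m = 100 |
|---|---|---|---|---|
| 0.05 | 0.071 | 0.036–0.069 | 0.022 | 0.045–0.055 |
| 0.10 | 0.100 | 0.031–0.078 | 0.032 | 0.043–0.058 |
| 0.20 | 0.141 | 0.025–0.092 | 0.045 | 0.041–0.061 |
| 0.30 | 0.173 | 0.021–0.105 | 0.055 | 0.039–0.064 |

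**Simulation at N = 75.** This used two-subgroup monotone regression imputation, ANCOVA, Rubin pooling and small-sample degrees of freedom, with 5 simulated trials per setting. The p ranges are for correlation 0.5; the shares cover both correlations.

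| Missing at Week 24 (assumed) | p range at stable p 0.05, m = 10 | Seeds with p > 0.05 at stable p 0.04, m = 10 | Same, m = 100 |
|---|---|---|---|
| 5% | 0.033–0.079 | 13–18% | about 0% |
| 10% | 0.031–0.086 | 21–23% | about 1% |
| 20% | 0.018–0.147 | 31–38% | 7–12% |
| 30% | 0.018–0.137 | 37–38% | about 10% |

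A separate simulation near a stable p of 0.04, with 4, 8 and 15 of 75 missing, gave SDs of t of about 0.08, 0.12 and 0.20 at m = 10. There, 14% to 31% of seeds gave p > 0.05. At m = 100 the SD was 0.03 to 0.06.

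**Cross-check by hand.** A p of 0.04 corresponds to t = 2.054, which is 0.094 above 1.96. With SDs of 0.08, 0.12 and 0.20, the share of seeds below 1.96 is Φ(−0.094/SD) = 12%, 22% and 32%, in line with the simulations.

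**Role of sample size.** In a further simulation at 10% missing, mean FMI was 0.15 at N = 75 and 0.08 at N = 600. Small N acts by raising FMI, not directly.

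**How often it would matter overall.** The chance that m = 10 and the stable analysis fall on opposite sides of 0.05 is about 0.80 × SD × (density of t at the threshold). For SDs of 0.08 to 0.20:
- At the design effect the density is φ(1.96 − 2.92) = 0.25, giving about 2% to 4%.
- Under no effect it is 2 × φ(1.96) = 0.117, giving about 1% to 2%.
- At m = 100 (SD 0.03 to 0.06), the design-effect figure falls to about 0.6% to 1.2%.

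**Limits.** These calculations fit the second-stage model within each imputed dataset. They do not reproduce Step 1 MCMC for intermittent gaps, or a stacked second-stage fit.

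**The case against.** The strongest reply is that the plan does not commit to 10. The code is labelled an example, and SAP 7.4.1 asks only for an appropriate procedure. The seed is written in all three steps, so if the code is used unchanged the p-value is reproducible and nobody chooses a seed after seeing the data. Rubin pooling already allows for finite m, and relative efficiency, 1/(1 + FMI/m), is 97% to 99.5% at m = 10 for FMI 0.30 to 0.05. The trial is a proof-of-concept phase 2 study, a seed-free LOCF analysis is planned, and the problem arises only for borderline results.

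Most of this stands, and it sets the size of the point. A reader might infer that m = 10 biases the result or inflates type I error. It does neither. A reader might also infer that the analysis is open to a choice of seed. The written seed argues against that, although it appears only in example code.

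Three things are not answered. A reproducible p-value can still be arbitrary, since seed 007 has no special standing. Relative efficiency describes the variance of the estimate, not the stability of a p-value near 0.05. LOCF answers a different question and cannot show Monte Carlo error.

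A further objection is correct: raising `nimpute` alone is not a complete fix. Without a BY statement, Steps 2a and 2b would fit one model to the stacked Step 1 copies: 10 now, 100 after the change.

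**Conclusion.** The point holds as a minor, free improvement. If Week 24 sPCR is missing for an assumed 5% to 20% of subjects, the pooled t at m = 10 has a seed-to-seed SD of about 0.08 to 0.20. A result with a stable p near 0.04 would be reported above 0.05 for roughly 15% to 35% of seeds.

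That share is conditional on a borderline result and is not an error rate of the trial. Over all possible trials at the design effect, the conclusion would change in only about 2% to 4%. The size rests on the assumed missing share, visit correlations and dropout pattern, and on few simulated trials per setting. The direction was the same at every missing share tried, from 5% to 30%. With complete Week 24 data, or a result far from 0.05, nothing changes.

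**What to change.** In SAP 7.4.1 and Appendix E:
- Set m to at least 100, or to a number that meets a stated Monte Carlo error limit. The limit is safer, because at 20% to 30% missing and a stable p of 0.04, 7% to 12% of seeds still cross 0.05 at m = 100.
- Fix the seed in the SAP text as well as in the code, before the final unblinding.
- Report the Monte Carlo error of the pooled estimate and of the p-value.
- Add `BY _Imputation_` to Steps 2a and 2b, so that each second-stage model is fitted within one imputed dataset. Make this change together with the new m.

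The cost is a small code edit and a little computing time at N = 75. No subject, visit or timeline is affected.
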